5.7 Subject Discontinuation

Subjects will receive study treatment until treatment discontinuation for one of the reasons listed below. However, subjects may discontinue study treatment or withdraw their consent to participate in the study at any time without prejudice. All reasons for discontinuation or withdrawal from trial will be recorded.

The maximum duration of treatment for pembrolizumab will be up to 35 cycles. The duration of treatment for XELOX will be until unacceptable drug-related toxicity or disease progression. If capecitabine is not tolerated, monotherapy with pembrolizumab may be continued. Patients who complete 35 cycles of therapy and have complete response or prolonged stable disease may also elect to end therapy with capecitabine after a discussion with their treating physician and with approval of the PI. Re-introduction of oxaliplatin is permitted provided that neuropathy has improved. Reasons for subject discontinuation by the Investigator may include, but are not limited to, the following:

- Death
- Confirmed radiographic disease progression (Note: With approval of the Lead PI, a subject may be granted an exception to continue on study treatment with confirmed radiographic progression if clinically stable or clinically improved.)
- Significant noncompliance by subject or Investigator
- Investigator or Lead PI determination that it is no longer safe and/or no longer in the subject's best interest to continue participation
- Withdrawal of consent
- Lost to follow-up
- Necessity for treatment with other anticancer treatment prohibited by protocol
- Sexually active subjects who refuse to use medically accepted methods of contraception during the course of the study and for 120 days following the last dose of study drug
- Women who become pregnant or are breast feeding
- Request by regulatory agencies for termination of treatment of an individual subject or all subjects under the protocol
- The following **Treatment-Related Discontinuation Criteria** attributed to pembrolizumab:
 - Any Grade 2 uveitis, eye pain, or blurred vision that does not respond to topical therapy and does not improve to Grade 1 OR requires systemic treatment.
 - Recurrent Grade 2 pneumonitis
 - Any Grade 3 non-skin adverse event lasting > 7 days, with the following exceptions for treatment-related laboratory abnormalities, uveitis, pneumonitis, bronchospasm, diarrhea, colitis, neurologic toxicity, hypersensitivity reactions, and infusion reactions:

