 - Grade 3 uveitis, pneumonitis, bronchospasm, diarrhea, colitis, neurologic toxicity, hypersensitivity reaction, or infusion reaction of *any duration* requires discontinuation
 - Grade 3 laboratory abnormalities do not require treatment discontinuation except Grade 3 thrombocytopenia > 7 days OR associated with bleeding requires discontinuation
 - Any liver function test (LFT) abnormality that meets the following criteria:

- AST or ALT > 8 x ULN
- Total bilirubin > 5 x ULN
- Concurrent AST or ALT > 3 x ULN and total bilirubin > 2 x ULN
- Any Grade 4 adverse event or laboratory abnormality, except for the following events:
 - Grade 4 amylase or lipase abnormalities that are not associated with symptoms or clinical manifestations, or radiographic signs of pancreatitis
 - Isolated Grade 4 electrolyte imbalances/abnormalities that are not associated with clinical sequelae and are corrected with supplementation/appropriate management within 3 days of their onset
 - Grade 4 endocrinopathy adverse events such as adrenal insufficiency, ACTH deficiency, hyper- or hypothyroidosis, or glucose intolerance, which resolve or are adequately controlled with physiologic hormone replacement (steroids, thyroid hormones) or glucose controlling agents, respectively, retreatment can be considered
- Any dosing interruption lasting > 6 weeks with the following exceptions:
 - Dosing interruptions to allow for prolonged steroid tapers to manage treatment-related adverse events are allowed
 - Dosing interruptions > 6 weeks that occur for non-treatment-related reasons may be allowed
- Any adverse event, laboratory abnormality, or intercurrent illness which, in the judgment of the Investigator, presents a substantial clinical risk to the subject with continued pembrolizumab or lanreotide depot dosing

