7.1.1 Pembrolizumab Dose Modifications

Adverse events (both non-serious and serious) associated with pembrolizumab exposure may represent an immunologic etiology. These adverse events may occur shortly after the first dose or several months after the last dose of treatment.

Pembrolizumab must be withheld for treatment-related toxicities as per Table 7.1.1. There are no dose reductions for pembrolizumab.

Note: Subject must be permanently discontinued for any severe or Grade 3 treatment-related toxicity that recurs or any life-threatening event unless otherwise specified in Table 7.1.1.

General Instructions:

1. Corticosteroid taper should be initiated upon AE improving to Grade 1 or less and continue to taper over at least 4 weeks.
2. For situations where pembrolizumab has been withheld, pembrolizumab can be resumed after AE has been reduced to Grade 1 or 0 and corticosteroid has been tapered. Pembrolizumab should be permanently discontinued if AE does not resolve within 12 weeks of last dose or corticosteroids cannot be reduced to ≤ 10 mg prednisone or equivalent per day within 12 weeks.
3. For severe and life-threatening irAEs, IV corticosteroid should be initiated first followed by oral steroid. Other immunosuppressive treatment should be initiated first followed by oral steroid. Other immunosuppressive treatment should be initiated if irAEs cannot be controlled by corticosteroids.

Table 7.1.1 Pembrolizumab Dose Modifications

Immune-related AEs	Toxicity grade or conditions (CTCAEv4.0)	Action taken to pembrolizumab	irAE management with corticosteroid and/or other therapies	Monitor and follow-up
Pneumonitis	Grade 2	Withhold	
 • Administer corticosteroids (initial dose of 1-2 mg/kg prednisone or equivalent) followed by taper 	
 • Monitor participants for signs and symptoms of pneumonitis • Evaluate participants with suspected pneumonitis with radiographic imaging and initiate corticosteroid treatment • Add prophylactic antibiotics for opportunistic infections
	Grade 3 or 4, or recurrent Grade 2	Permanently discontinue		

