Diarrhea / Colitis	Grade 2 or 3	Withhold	
 • Administer corticosteroids (initial dose of 1-2 mg/kg prednisone or equivalent) followed by taper 	
 • Monitor participants for signs and symptoms of enterocolitis (ie, diarrhea, abdominal pain, blood or mucus in stool with or without fever) and of bowel perforation
	Grade 4	Permanently discontinue		

Immune-related AEs	Toxicity grade or conditions (CTCAEv4.0)	Action taken to pembrolizumab	irAE management with corticosteroid and/or other therapies	Monitor and follow-up
				
(ie, peritoneal signs and ileus).
 
 Participants with \geq Grade 2 diarrhea suspecting colitis should consider GI consultation and performing endoscopy to rule out colitis. Participants with diarrhea/colitis should be advised to drink liberal quantities of clear fluids. If sufficient oral fluid intake is not feasible, fluid and electrolytes should be substituted via IV infusion.
AST / ALT elevation or Increased bilirubin	Grade 2	Withhold	Administer corticosteroids (initial dose of 0.5- 1 mg/kg prednisone or equivalent) followed by taper	Monitor with liver function tests (consider weekly or more frequently until liver enzyme value returned to baseline or is stable)
	Grade 3 or 4	Permanently discontinue	Administer corticosteroids (initial dose of 1-2 mg/kg prednisone or equivalent) followed by taper	
Type 1 diabetes mellitus (T1DM) or Hyperglycemia	Newly onset T1DM or Grade 3 or 4 hyperglycemia associated with evidence of β -cell failure	Withhold	
 Initiate insulin replacement therapy for participants with T1DM Administer anti-hyperglycemic in participants with hyperglycemia 	
 Monitor participants for hyperglycemia or other signs and symptoms of diabetes.
Hypophysitis	Grade 2	Withhold	
 Administer corticosteroids and initiate hormonal replacements as clinically indicated. 	
 Monitor for signs and symptoms of hypophysitis (including hypopituitarism and adrenal insufficiency)
	Grade 3 or 4	Withhold or permanently discontinue ¹		
Hyperthyroidism	Grade 2	Continue	Treat with non-selective beta-blockers (eg, propranolol) or thionamides as appropriate	
 Monitor for signs and symptoms of thyroid disorders.
	Grade 3 or 4	Withhold or permanently discontinue ¹		

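### Section 5.7 and the hepatic row of Table 7.1.1 print different pembrolizumab stopping rules, so a patient who meets Section 5.7's concurrent AST/ALT and bilirubin criterion can be re-treated under the table

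*Combined protocol and SAP*

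**What the plan says.** **Section 5.7 (Subject Discontinuation)** has a sub-list of treatment-related criteria attributed to pembrolizumab.

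- It covers "Any liver function test (LFT) abnormality that meets the following criteria". The three criteria are "AST or ALT > 8 x ULN", total bilirubin above 5 x ULN, and "Concurrent AST or ALT > 3 x ULN and total bilirubin > 2 x ULN".
- A separate bullet covers "Any Grade 3 non-skin adverse event lasting > 7 days, with the following exceptions for treatment-related laboratory abnormalities". Under it stands the exemption "Grade 3 laboratory abnormalities do not require treatment discontinuation except Grade 3 thrombocytopenia" (prolonged or with bleeding).
- Any Grade 4 laboratory abnormality is also listed, with exceptions that do not concern liver tests.
- The whole list opens with "Reasons for subject discontinuation by the Investigator may include, but are not limited to, the following".

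**Section 7.1.1** says "Pembrolizumab must be withheld for treatment-related toxicities as per Table 7.1.1". In that table the row "AST / ALT elevation or Increased bilirubin" has two levels: withhold at Grade 2, permanently discontinue at Grade 3 or 4. It has no multiples of ULN and no criterion for a concurrent rise. The general instructions above the table allow a withheld patient to resume once the event is at Grade 0 or 1 and steroids have been tapered.

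**Links between the two.** Section 5.2 sends the reader to Section 5.7 for reasons to discontinue and to Section 7.1 for dose modification, and does not rank them. Section 7.2.6 (Hepatic) covers monitoring and steroids and has no stopping rule. Under Section 7.1, permanent discontinuation of pembrolizumab takes the patient off all study treatment.

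**The concern.** Both sections apply to a liver-test rise attributed to pembrolizumab, and a site may consult either one when the result arrives.

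The concurrent rise matters more. Section 5.7 singles out a combined transaminase and bilirubin rise as a reason to stop at levels where neither value alone would be one. A site working from the table finds only a withhold instruction and a route back to dosing. It can therefore re-treat a patient who meets a printed stopping criterion.

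The isolated rise runs the other way. A site that relies on Section 5.7 may think that continuing is acceptable where the mandatory table stops the drug.

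**Working it through.** There is no planned figure to reproduce. The check applies both rules to the same pairs of values.

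**Inputs.** A = AST or ALT and B = total bilirubin, both in multiples of ULN. The Section 5.7 cut-offs are printed. Table 7.1.1 is headed with CTCAE v4.0, whose liver limits the documents do not print. Assumed limits: AST/ALT Grade 2 > 3 to 5, Grade 3 > 5 to 20; bilirubin Grade 2 > 1.5 to 3, Grade 3 > 3 to 10.

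**Rules.**
- Section 5.7 stops if A > 8, or B > 5, or (A > 3 and B > 2). Its Grade 4 criterion adds nothing under these limits, because Grade 4 starts at 20 x and 10 x, beyond the cut-offs.
- Table 7.1.1 stops if A > 5 or B > 3. It withholds if neither holds but A > 3 or B > 1.5.

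**Gap 1: the table stops, Section 5.7 does not require it.** This needs (A > 5 or B > 3), with A ≤ 8, B ≤ 5 and the concurrent rule not met.
- If A is above 5, it is also above 3, so B must be ≤ 2. Zone: A > 5 to 8 with B ≤ 2.
- If B is above 3, it is also above 2, so A must be ≤ 3. Zone: B > 3 to 5 with A ≤ 3.

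**Gap 2: Section 5.7 stops, the table only withholds.** This needs A ≤ 5 and B ≤ 3 with (A > 3 and B > 2). Zone: A > 3 to 5 with B > 2 to 3.

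| A (x ULN) | B (x ULN) | Section 5.7 | Table 7.1.1 | Same? |
|---|---|---|---|---|
| 6 | 1 | not required | stop | no (gap 1) |
| 7.9 | 1 | not required | stop | no (gap 1) |
| 9 | 1 | stop | stop | yes |
| 1 | 4 | not required | stop | no (gap 1) |
| 1 | 6 | stop | stop | yes |
| 4 | 2.5 | stop | withhold | no (gap 2) |
| 4.9 | 2.9 | stop | withhold | no (gap 2) |
| 4 | 1.8 | not required | withhold | no stop in either |
| 6 | 2.5 | stop | stop | yes |

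**Sensitivity to the assumed limits.**
- Gap 1 exists whenever Grade 3 starts below 8 x ULN (AST/ALT) or below 5 x ULN (bilirubin).
- Gap 2 exists only if Grade 3 starts above 3 x ULN for AST/ALT and above 2 x ULN for bilirubin.
- The one bilirubin scale that the protocol prints is in the capecitabine label text of Section 1.2.3 (Grade 3 = 1.5 to 3 x, Grade 4 > 3 x ULN). On that scale gap 2 disappears, and the bilirubin part of gap 1 moves to > 1.5 to 3 x ULN. Table 7.1.1 does not use that scale.

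**The case against.** The strongest defence is that the sections add to each other. Section 5.7's list is expressly open-ended. Its exemption says only that stopping is not required, and only as an exception to the criterion on Grade 3 events lasting over 7 days; it never tells a site to continue. The table is mandatory, so a site bound by the whole protocol stops in gap 1. In gap 2 the table's withhold does not bar stopping and resumption is optional, so discontinuing again satisfies both. Section 5.2 supports this by making Section 5.7 operative beside Section 7.1. Hence a reader who infers that a site cannot comply with both texts goes too far.

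There are safeguards as well. Section 7.1 lets investigators depart from the dose tables for safety. Section 5.7 allows discontinuation when the investigator or Lead PI judges continuation unsafe, or when the investigator sees a substantial clinical risk. Under Section 10.3, hepatic toxicity of Grade 2 or higher is an event of clinical interest: external sites send the form to the coordinating team within 24 hours and the Lead PI reviews it. Every gap 1 or gap 2 patient qualifies under the assumed limits.

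The scopes also differ in label: the table is for immune-related events, Section 5.7 for events attributed to pembrolizumab. They still overlap for an immune-related liver rise attributed to the drug.

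Most of this stands and lowers the severity. What remains is that no text tells a site to apply whichever rule stops the drug, and the Lead PI who reviews the form reads the same two rules.

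**Conclusion.** The two sections print different hepatic stopping rules for overlapping events. Gap 1 (isolated Grade 3 values up to 8 x ULN for AST/ALT or 5 x ULN for bilirubin) is a misleading inconsistency and not a strict contradiction. Gap 2 (concurrent rise, both values Grade 2) is the part with a safety consequence, because the table leaves open re-treatment of a patient whom Section 5.7 lists for stopping. Gap 2 rests on CTCAE v4.0 limits that the table names and the documents do not print. Not every concurrent Grade 2 rise is affected, only those with AST/ALT above 3 x and bilirubin above 2 x ULN.

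The number of patients cannot be derived from the documents; few are expected among 35. Power and alpha are untouched. A reader might infer that PFS would be distorted, since Section 9.1.1 ties entry to the primary analysis to an on-treatment restaging or earlier unequivocal progression. That would need one of these uncommon events before the first restaging, and the documents give no basis for more than a negligible effect. A reader might also infer from the entry limit of 5 x ULN with liver metastases that baseline-relative rules are needed. Both sections require attribution to treatment, so a high entry value alone triggers neither, and the documents supply no number for such a rule.

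This is a minor safety-conduct correction.

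**What to change.** Three wording changes in one amendment:

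1. In the hepatic row of Table 7.1.1, add the criterion "Concurrent AST or ALT > 3 x ULN and total bilirubin > 2 x ULN" with the action *permanently discontinue*.
2. In the Section 5.7 exemption for Grade 3 laboratory abnormalities, add *except AST/ALT or bilirubin, for which Table 7.1.1 also applies*.
3. In both sections, state that meeting either section's criterion requires permanent discontinuation of pembrolizumab.

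No visits, tests or patients are added; the amendment needs the usual ethics approval under Section 11.2. The downside is that sites which relied on the Section 5.7 exemption will stop a few patients with isolated Grade 3 values. Under Section 7.1 those patients then lose all study treatment, although the table already requires this.

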6.0 STUDY DRUGS

6.1 Treatment Compliance and Study Drug Accountability

The Investigator will maintain accurate records of receipt of all study drugs, including dates of receipt. In addition, accurate records will be kept regarding when and how much study drug is dispensed and used by each subject in the study. Reasons for deviation from the expected dispensing regimen must also be recorded. At completion of the study, to satisfy regulatory requirements regarding drug accountability, all unused study drug will be reconciled and destroyed in accordance with applicable state and federal regulations.

6.2 Pembrolizumab

Pembrolizumab will be provided for this study by Merck & Co., a sterile, non-pyrogenic lyophilized powder for intravenous infusion supplied in single-use Type I glass vial containing 50 mg of pembrolizumab. The product is preservative-free, white to off-white powder and free from visible foreign matter. It is reconstituted with 2.3 mL sterile water for injection (WFI) to yield a 2.4 mL solution containing 25 mg/mL of pembrolizumab. The reconstituted vial contains an excess fill of 10 mg (equivalent to 0.4 mL of reconstituted solution) to ensure the recovery of label claim of 50 mg pembrolizumab per vial (equivalent to 2 mL of reconstituted solution).

6.2.1 Storage and Handling

Pembrolizumab Powder for Solution for Infusion vials should be stored at refrigerated conditions (2-8 °C). Prior to reconstitution, the vial of lyophilized powder can be out of refrigeration (temperatures at or below 25°C (77°F) for up to 24 hours. Following reconstitution with sterile water for injection, Pembrolizumab infusion solutions should be prepared in 0.9% Sodium Chloride Injection, USP (normal saline) or regional equivalent and the final concentration of pembrolizumab in the infusion solutions should be between 1 mg/mL and 10 mg/mL. If normal saline is not available, 5% Dextrose Injection, USP or regional equivalent (5% dextrose) is permissible. The preferred diluent is 0.9% Sodium Chloride and 5% dextrose is only permissible if normal saline is not available.

Pembrolizumab solutions may be stored at room temperature for a cumulative time of up to 4 hours. This includes room temperature storage of reconstituted drug product solution in vials, room temperature storage of admixture solutions in the IV bags and the duration of infusion. In addition, reconstituted vials and/or IV bags may be stored under refrigeration at 2 °C to 8 °C (36 °F to 46 °F) for up to 20 hours. If refrigerated, allow the vials and/or IV bags to come to room temperature prior to use.

Refer to Pembrolizumab Pharmacy Manual for additional drug product stability and handling guidelines.

6.2.2 Administration

Pembrolizumab 200 mg will be administered in an outpatient setting as a 30-minute IV infusion on Days 1 of each cycle. A treatment window of +/- 3 days of day 1 is allowed for cycle 2 and all subsequent cycles. Every effort should be made to target infusion timing to be as close to 30 minutes as possible. However, given the variability of infusion pumps, a window of -5 minutes and +10 minutes is permitted (i.e., infusion time is 30 minutes: -5 min/+10 min).

It is preferred, but not mandatory, that pembrolizumab be administered after oxaliplatin infusion.

Refer to Pembrolizumab Pharmacy Manual specific instructions for the preparation of the pembrolizumab infusion fluid and administration of infusion solution.

6.3 Oxaliplatin

Oxaliplatin will be obtained from commercial sources; the cost of oxaliplatin and its infusion will be billed to the subject and/or subject's insurance.

Oxaliplatin for injection and oxaliplatin injection) is an antineoplastic agent with the molecular formula C8H14N2O4Pt and the chemical name of cis-[(1 R,2 R)-1,2 cyclohexanediamine-N,N'] [oxalato(2)-O,O'] platinum. Oxaliplatin is an organoplatinum complex in which the platinum atom is complexed with 1,2-diaminocyclohexane(DACH) and with an oxalate ligand as a leaving group. The molecular weight is 397.3. Oxaliplatin is slightly soluble in water at 6 mg/mL, very slightly soluble in methanol, and practically insoluble in ethanol and acetone.

Powder for solution for infusion: Oxaliplatin is supplied in vials containing 50 mg or 100 mg of oxaliplatin as a sterile, preservative-free lyophilized powder for reconstitution. Lactose monohydrate is present as an inactive ingredient at 450 mg and 900 mg in the 50 mg and 100 mg dosage strengths, respectively.

Concentrate for solution for infusion: Oxaliplatin is supplied in vials containing 50 mg, 100 mg or 200 mg of oxaliplatin as a sterile, preservative-free, aqueous solution at a concentration of 5 mg/ml. Water for Injection, USP is present as an inactive ingredient.

6.3.1 Storage and Handling

Powder for Solution for Infusion

Reconstitution or final dilution must never be performed with a sodium chloride solution or other chloride containing solutions. The lyophilized powder is reconstituted by adding 10 mL (for the 50 mg vial) or 20 mL (for the 100 mg vial) of Water for Injection, USP or 5% Dextrose Injection, USP. Do not administer the reconstituted solution without further dilution. The reconstituted solution must be further diluted in an infusion solution of 250-500 mL of 5% Dextrose Injection, USP. After reconstitution in the original vial, the solution may be stored up to 24 hours under refrigeration [2-8°C (36-46°F)]. After final dilution with 250-500 mL of 5% Dextrose Injection, USP, the shelf life is 6 hours at room temperature [20-25°C (68-77°F)] or up to 24 hours under refrigeration [2-8°C (36-46°F)]. Oxaliplatin is not light sensitive.

Concentrate for Solution for Infusion

Do not freeze and protect from light the concentrated solution. A final dilution must never be performed with a sodium chloride solution or other chloride-containing solutions. The solution must be further diluted in an infusion solution of 250-500 mL of 5% Dextrose Injection, USP. After dilution with 250-500 mL of 5% Dextrose Injection, USP, the shelf life is 6 hours at room temperature [20-25°C (68-77°F)] or up to 24 hours under refrigeration [2-8°C (36-46°F)]. After final dilution, protection from light is not required.

Incompatibilities

Oxaliplatin is incompatible in solution with alkaline medications or media (such as basic solutions of 5-fluorouracil) and must not be mixed with these or administered simultaneously through the same infusion line. The infusion line should be flushed with 5% Dextrose Injection, USP prior to administration of any concomitant medication.

Parenteral drug products should be inspected visually for particulate matter and discoloration prior to administration and discarded if present.

Needles or intravenous administration sets containing aluminum parts that may come in contact with oxaliplatin should not be used for the preparation or mixing of the drug. Aluminum has been reported to cause degradation of platinum compounds.

As with other potentially toxic anticancer agents, care should be exercised in the handling and preparation of infusion solutions prepared from oxaliplatin. The use of gloves is recommended. If a solution of oxaliplatin contacts the skin, wash the skin immediately and thoroughly with soap and water. If oxaliplatin contacts the mucous membranes, flush thoroughly with water.

